10.3 HRQoL instrument

Quality of life will be assessed using an ad-hoc questionnaire based on the EORTC Quality of Life Questionnaire (QLQ-C30) version 3. This instrument is composed of multi-item and single-item scales. These include five functional scales (physical, role, emotional, social, and cognitive), three symptoms (fatigue, nausea and vomiting and pain) and a global health status/QoL scale and six single items (dyspnea, insomnia, appetite loss, constipation, diarrhea and financial difficulties). All scales and single items meet the standards for reliability. The reliability and validity of the questionnaire is highly consistent across different language-cultural groups (Ref. 50). The average time to complete the questionnaire is approximately 10 minutes. The EORTC QLQ-C30 version 3 has been translated in over 50 languages according to a standardized translation procedure. While this questionnaire is the most used instrument in cancer clinical trials (Ref. 51), it contains some superfluous dimensions while lacking some particular to the QL issues in certain brain cancer. Therefore, the instrument was modified by removing unneeded questions and shortening certain scales by using the equivalent from the PAL15 instrument (Ref. 52). Relevant items were added, mainly from the EORTC Brain Cancer module (QLQ-BN20) (Ref. 53), designed for use in patients undergoing protocol treatment or radiotherapy and from the QLQ-STO22 (Ref. 54).

The final modified questionnaire consists of the EORTC QLQ-C30 version 3 with the following changes:

- Financial difficulties scale removed (-1 question).
- Physical functioning replaced by PAL15 version (-2 questions)
- Emotional functioning replaced by PAL15 version (-2 questions)
- Motor Dysfunction added from BN20 (+3 questions)
- Cognitive Deficit added from BN20 (+3 questions)
- Drowsiness added from BN20 (+1 question)
- Headaches added from BN20 (+1 question)
- Seizures added from BN20 (+1 question)
- Abdominal Pain added from STO22 (+1 question)

All modifications were done using the EORTC Item Library to ensure content validity and adequate translations of the added questions.

10.4 Study design

Patients in Group A and Group B who are eligible for the HRQoL assessment in this study if they fulfill the eligibility criteria (see chapter 3). Should the HRQoL forms not be available in the required language or should the patient refuse to fill out the form, then this should exclude the patient from further participation in the study. Patients will be informed in the patient informed consent form that they will have their quality of life assessed regularly while involved in this trial. In this phase Ib part of study 1608, HRQoL will be an exploratory outcome and evaluated in a longitudinal design in all patients entered in arms A and B of the study.

HRQoL questionnaires must be filled out at the hospital according to the EORTC “Guidelines for administration of questionnaires” (see Appendix F) when patients come for a scheduled visit for a complete neurological examination (NANO). The pre-treatment questionnaires must be filled out within 14 days before enrollment. Subsequent questionnaires are administered at the end of every second cycle (\pm 8 days) until cycle 6, then at the end of every third cycle (\pm 8 days), at the end of study visit, and every 3 months (\pm 14 days) afterwards until death or patient refusal.

The time windows for eligible HRQoL assessments will be as follows:

Assessment	Time window
Baseline	Can be completed before or on the day of randomization itself but no earlier than 2 weeks before.
End of cycle 2	Can be 8 days before or after D1 of cycle 3
End of cycle 4	Can be 8 days before or after D1 of cycle 5
End of cycle 6	Can be 8 days before or after D1 of cycle 7
End of cycle 9 + q3W	Can be 8 days before or after D1 of every 3rd cycle after cycle 7 (i.e. cycle 10, 13, 16, ...).
End of study visit	End of study visit should take place within 30 days after the last dose of TG02.
Follow-up after end of study treatment	Every 3 months (\pm 14 days)

Master copies of the HRQoL questionnaires will be sent to the institutions. Additional copies or translations can be provided upon request via the EORTC contact person. The clinical report forms will include a question whether the HRQoL forms have been filled in, and if not, the reason why. The questionnaire will be handed out to the patients by the investigator or a study nurse prior to seeing the doctor for clinical evaluations. The patient should complete the questionnaires by her/himself in her/his own language during the visit as completely and accurately as possible. It is recommended that a key person (e.g. research nurse) at each center should be responsible for questionnaire data collection in order to optimize the compliance of the patient and to ensure the completeness of the data.

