2.2.2 Secondary endpoints

Groups A and B:

- progression-free survival at 6 months (PFS-6)
- median progression-free survival (PFS)
- median overall survival (OS)
- OS at 9 months (OS-9)
- for patients with measurable disease after debulking: best overall response distribution (BOR), objective response rate (PR+CR), complete response rate and duration of response (DOR)
- quality of life (QOL)

Group C:

- median progression-free survival (PFS)
- median overall survival (OS)
- OS at 9 months (OS-9), 1 year (OS-12)
- for non-surgical patients or patients with surgery for recurrence, but measurable disease thereafter: best overall response distribution (BOR), objective (PR+CR) rate, complete response rate and duration of response (DOR)
- success rate defined as rate of patients achieving either confirmed CR or PR (> 4 weeks) or free of progression at 6 months
- neurological progression-free survival (NPFS) based on the Neurologic Assessment in Neuro-Oncology (NANO): median NPFS and NPFS at 6 months (NPFS-6).
- clinical deterioration free survival (CDFS).
- safety profile (CTCAE)

pharmacokinetic profile of TG02: pre-dose, 30 minutes, 1 hour, 2 hours, 4 hours, 8 hours and 24 hours after the intake of TG02

In all groups:

- Correlation of molecular markers including MYC, MCL-1, CDK9 and CDK5 protein levels, and potentially others, with measures of clinical benefit.

3 Patient selection criteria

Patients must fulfill all of the following criteria to be eligible for registration in the study:

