8.1 Statistical design

8.1.1 Sample size

Groups A and B

This is an open label, non-randomized, multi-center trial using the classical 3+3 design.

In both groups A and B, a minimum of 3 patients will be included at each dose level. There is no intention to increase the dose of TG02 above 150 mg in Groups A and B. Within one dose level, patients may be entered simultaneously. The second dose level may be started when all patients of dose level 1 have completed cycle 1 (28 days).

In case of occurrence of 1 DLT, an additional 3 patients will be added in order to ensure the safety profile of this dose level unless a DLT is documented immediately in any additional patient entered at this dose level. If 2 DLT are observed in the first 3 patients dose escalation will stop without need to extend the dose level to 6 patients.

The replacement of patients will be performed in case of patients that progress, die due to disease progression, or leave study for any reason other than DLT prior to completion of the first cycle of therapy.

After determination of the MTD, additional patients will be treated at the highest dose level for additional safety information in the absence of safety issues up to a total of 24 evaluable patients in Group A and up to a total of 12 evaluable patients in Group B (up to 36 evaluable patients for Groups A and B). We consider groups A and B exploratory and independent from each other, with the prime goal of assessing feasibility (tolerability, safety). The difference in size in these two groups reflects the natural distribution of patients into those with tumors without (2/3, group A) and with (1/3, group B) MGMT promoter methylation. The elderly patient population is ideally suited to explore safety, tolerability and efficacy of TG02 with the two backbones of glioblastoma treatment, radiotherapy (group A) and temozolomide (group B), in isolation. Finally, there is a feasibility consideration: we anticipate that doctors and patients are more willing to omit temozolomide in group A than to omit radiotherapy in arm B although such a strategy is consistent with the EANO guideline updated in 2017 (Ref. 35).

Number of Patients with DLT at a Dose Level	Dose Escalation Decision Rule in Groups A and B
0 out of 3	Enroll 3 patients at the next dose level up to a maximum TG02 dose of 150 mg.

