10.2 Objective

Since elderly patients are more prone to side-effects from novel treatments and since maintaining HRQoL is a major consideration in de-escalating treatments that provide little benefit, e.g., TMZ in patients with tumors without MGMT promoter methylation, this phase Ib trial will also capture data on HRQoL in Group A (addition of TG02 to postoperative RT in MGMT-unmethylated, IDH1^{R132H}-non-mutant WHO grade III and IV glioma) and B (addition of TG02 to postoperative TMZ chemotherapy in MGMT-methylated IDH1^{R132H}-non-mutant WHO grade III and IV glioma). Therefore, in the present study, HRQoL is an exploratory endpoint.

The main objective of this study is to explore the impact of combined treatment on overall global health and HRQoL in this fragile, elderly (> 65 years) high-grade glioma patient population. A secondary objective is to evaluate the effect of the treatment on the remaining symptoms and functioning scales as treatment-related side-effects may have a (temporary) negative influence on the health related domains of HRQoL of these patients with a particular emphasis on fatigue, nausea/vomiting and diarrhea in the light of the expected side effects of TG02.

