Appendix F: EORTC Quality of Life evaluation: guidelines for administration of questionnaires

EORTC Quality of Life evaluation: guidelines for administration of questionnaires

The instructions given below are intended to provide some general guidelines for collecting quality of life (QOL) data in EORTC studies. These instructions apply for all types of questionnaires.

1. Who is the responsible person (RP) for QOL data collection?

In each institution, the principal investigator is the responsible for the local organization of QOL data collection. This can be delegated to a physician, data manager, (research) nurse or a psychologist. Such a person should have the full protocol at his/her disposal as well as the questionnaire(s). This person would also be the intermediate contact point in case of any necessary clarification asked by the EORTC Headquarters.

2. Who should fill out the questionnaire?

In principle it is the patient who has to complete the QOL forms and preferably without help from others. In the case where a patient is too sick to fill out the questionnaire by him/herself or if the patient is not able to complete the questionnaire for such reasons as forgetting his/her glasses, another person could read the questions without making any suggestions and report the answers on the forms. It is not allowed for another person to fill in the questionnaire as if (s)he was the patient (proxy assessment) unless specifically allowed by the protocol.

3. What instructions should be given to the patient?

At entry in a study, the RP should give the patient an explanation of the objective of the study and instructions for completing the questionnaires.

The patient should be informed that participation in the QOL protocol is voluntary and that the information provided is confidential (identification is only for administrative purposes and includes date of birth and today's date (completion date)).

The following issues should be explained to the patient:

- The schedule of assessments.
- The questionnaire is a self-administered questionnaire that should be completed by the patient him(her)self. The patient can ask for aid in reading or writing but should not let another person provide the answers.
- The patient should circle the choice that best corresponds to his/her situation.
- There is no right or wrong answer to any of these questions. The answers will not influence any medical decision making.
- All questions should be answered.

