- The patient will be given a questionnaire in the default language(s) of the hospital. If desired, the patient may request another language. The RP will then contact the EORTC Headquarters for the appropriate translation.

The RP should make sure that the patient understands the instructions.

At each subsequent assessment as defined by the protocol, the patient should receive the questionnaire from the RP or from other appropriate staff if the RP is unavailable.

4. Where should the patient complete the questionnaire?

The patient should complete the questionnaire at the clinic, and, ideally in a quiet, private room. If this is not possible, the waiting room is an acceptable alternative. In general it does not take long to complete the questionnaire, but patients should be given the time they need to answer all questions.

5. When should they complete the questionnaire?

The timing of the planned QoL assessments is detailed in the protocol. When a QOL assessment is planned, the questionnaire should be given to the patient preferably before the meeting with the physician, ensuring that the patient has enough time to complete the questionnaire. If the patient is to receive a therapy, the questionnaire should be filled out before administration of the treatment (unless indicated otherwise in the protocol). The questionnaire should not be taken home and/or mailed (unless indicated otherwise in the protocol).

6. Review of the completed questionnaire

After the patient has completed the questionnaire, the person handling the questionnaire should:

- Complete the “Hospital Staff” specific data box.
- Check that the completion date is correctly filled in by the patient.
- Screen the questionnaire for omissions.

If this is the case:

- Please ask the patient the reason for omissions. It may be that patient forgot to flip a page or did not understand a question. The patient should not be forced to provide an answer if (s)he does not wish to do so.
- Additional explanation may be provided, but the questions should not be rephrased.

7. Missing forms

If for some reason the patient is unable or does not wish to complete a quality of life questionnaire the reason and the date of visit should be documented on the corresponding CRF (case report form).

8. Mailing to EORTC Headquarters

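### Section 10.4 excludes Group A and B patients from the study for refusing the quality-of-life form or lacking a translation of it, which the rest of the protocol contradicts

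*Combined protocol and SAP*

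**What the plan says.** Section 10.4 attaches one consequence to two triggers. The first is a missing translation: "Should the HRQoL forms not be available in the required language". The second is refusal: "or should the patient refuse to fill out the form, then this should exclude the patient from further participation in the study". The rule is not limited to the baseline form.

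The same chapter gives quality of life a modest role. Section 10.2 states: "Therefore, in the present study, HRQoL is an exploratory endpoint". Section 10.4 repeats that "HRQoL will be an exploratory outcome and evaluated in a longitudinal design in all patients entered in arms A and B". Section 2.2.2 and the synopsis instead list it among the secondary endpoints of Groups A and B, and section 2.1.2 makes it a secondary objective.

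Appendix F, which 10.4 cites as its guideline for administering the forms, takes the opposite line on refusal: "The patient should be informed that participation in the QOL protocol is voluntary". Its item on missing forms begins "If for some reason the patient is unable or does not wish to complete a quality of life questionnaire" and then asks only for the reason and the visit date on the CRF.

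**The concern.** As printed, a patient who meets every criterion in chapter 3 can be kept out of the trial, or taken out later, over a questionnaire that is not a primary endpoint under any label. Two sites could handle the same refusal in opposite ways and both cite the protocol. Patients are also to be told that this component is voluntary, while 10.4 makes their place in the trial depend on it.

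For the analysis, the stake is who enters Groups A and B and how long they are observed. Selection at entry narrows the population to which the tolerability results apply. Ending participation at a later refusal cuts short safety and progression follow-up. In these groups section 7.2.2 censors PFS at the last radiological assessment, so if refusal goes with deterioration, the censoring would be informative.

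**Working it through.** The plan states no figure on this point, so there is nothing to reproduce. The check compares the passages and then places the forms on the trial calendar.

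**1. What each place does with a form that is refused or missing**

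| Place | Handling |
|---|---|
| 10.4, exclusion sentence | Patient leaves the study |
| 10.4, schedule | Forms run until death or until the patient declines, so refusal ends form collection only |
| 10.4, CRF paragraph | The CRF asks whether the form was completed and, if not, why |
| 10.5.1 | Patients with and without valid data are compared; a fallback exists for compliance below 50% |
| Appendix F | Voluntary; the reason is recorded; no answer is to be forced |
| Chapter 3 | No criterion on form completion or form language |
| 5.4 | Refusing a form is not a named reason to discontinue; unnecessary withdrawals are to be avoided |

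Only the first row removes the patient. The others either assume that non-completers stay in the trial or give no ground for removing them.

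**2. When the rule can act**

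Inputs:
- The baseline form is due within 14 days before enrollment (10.4).
- The first on-treatment form is due at day 1 of cycle 3, ± 8 days (10.4 and 6.2.4.2).
- Cycle 1 lasts 28 days in Group A (6.2.1) and 35 days in Group B, counted from day -7 (6.2.2). Cycle 2 lasts 28 days.
- DLTs are counted in cycle 1 (5.2.1.1 and 5.2.1.2).
- Replacement covers patients who "leave study for any reason other than DLT prior to completion of the first cycle of therapy" (8.1.1).

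Nominal earliest on-treatment form, in days after the first TG02 dose = length of cycle 1 + 28 − 8:
- Group A: 28 + 28 − 8 = 48 days. Cycle 1 is complete at 28 days, so the gap is 48 − 28 = 20 days.
- Group B: 35 + 28 − 8 = 55 days. Cycle 1 is complete at 35 days, so the gap is 55 − 35 = 20 days.

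No scheduled on-treatment form falls inside cycle 1. The only earlier one is the end-of-study form of a patient who has already stopped treatment for another reason.

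**3. What follows at each time**
- *Before enrollment:* a refuser, or a patient with no translation, is not enrolled. This is an entry criterion that chapter 3 does not list.
- *From about cycle 3 day 1:* a refuser has completed the DLT period and stays in the safety population (8.2.1), on which all Group A and B analyses are run (8.2.2). What is lost is later observation, mainly safety and progression. Section 5.4 still asks for an end-of-study visit and survival follow-up where feasible.

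**4. Reach**

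Up to 24 evaluable patients in Group A and 12 in Group B (8.1.1), so 24 + 12 = 36. Group C completes no quality-of-life forms.

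**The case against.** **The rule may be intended.** A trial may make questionnaires compulsory. Section 10.4 says the consent form tells patients that quality of life will be assessed regularly, and section 3.1 requires agreement to return for required assessments. But that general criterion does not name the questionnaire and cannot cover a missing translation. An intended rule would also not sit beside Appendix F and 10.5.1 as they stand.

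**The study may mean the quality-of-life component.** Section 10.2 does use the word loosely when it states its main objective. Within 10.4, however, the word also covers the whole trial with its arms A and B. If the narrow sense was meant, the sentence still needs correcting.

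**The practical effect may be small.** This partly stands. The surrounding text points sites away from exclusion, translations can be requested, and section 10.3 puts the base questionnaire in over 50 languages.

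Three stronger inferences are tempting, and the documents do not support them:
- *That refusers are replaced in cycle 1, which distorts DLT counts.* The calendar above rules this out apart from rare cases.
- *That the rule removes the sickest patients.* Its triggers are refusal and language, not inability. Appendix F lets another person read out the questions and record the answers.
- *That a countable number of patients is lost.* A guessed 10–20% refusal rate applied to 36 gives 3.6 to 7.2, but no such rate appears in the documents. The 36 is a cap on evaluable patients, and baseline refusers never enter it. The 50% compliance figure in 10.5.1 switches the analysis; it is not a forecast of refusals.

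**Conclusion.** The exclusion sentence in 10.4 is wrong as written. It contradicts its own section, 10.5.1 and Appendix F, and it has no counterpart in chapter 3 or section 5.4. That a *not* was dropped is the likeliest explanation, but it is an inference from the surrounding text.

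Followed literally, the sentence creates an unlisted entry barrier and a reason to end participation at later forms. It could cause selection at entry and loss of later safety and progression follow-up in Groups A and B. It would seldom affect DLT counts or cycle 1 replacement, and the number of patients affected cannot be estimated from the documents. The case for correcting it rests on the contradiction itself.

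The conclusion does not depend on whether quality of life is exploratory (chapter 10) or secondary (section 2.2.2). That difference is a separate inconsistency, and under neither label is it a primary endpoint.

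**What to change.** Change 10.4 so that refusal, or the lack of a form in the required language, should *not* exclude the patient from further participation. Add that the reason is recorded on the CRF, as 10.4 and Appendix F already provide, and that the patient stays in study follow-up and in all safety and efficacy analyses.

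If exclusion really is intended, chapter 3 and section 5.4 must state it, say which forms it applies to, and be reconciled with Appendix F and 10.5.1.

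The cost is one word plus a clarifying sentence. No new data item, visit or sample-size change is needed.

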10.5 Statistical considerations

The primary HRQoL endpoint that is considered relevant for this study is the Global health/QoL status (GHQs) scale of the QLQ-C30 instrument. Other scales will be analyzed on an exploratory basis as secondary HRQoL endpoints, with a particular emphasis on fatigue and nausea/vomiting and diarrhea in the light of the expected side effects of TG02. The standard deviation of this scale is approximately 20

points. As this is an exploratory analysis in the framework of a phase 1b study with a sample size dependent on toxicity, using a classical phase I dose-escalation design (3+3), we do not provide a sample size calculation.

Data will be scored according to the algorithm described in the EORTC scoring manual (Ref. 55). All scales and single items are scored on categorical scales and linearly converted to 0-100 scales. Reporting of data will be mainly descriptive, as this is an exploratory analysis.

Changes in HRQoL scores over time will be evaluated with a repeated measurement modeling using a mixed effect procedure. A linear mixed model with treatment, a time effect, a time-treatment interaction and possibly other baseline covariates as fixed effects and a patient specific random effect will be fitted. Prior to reducing the model, the most suitable covariance structure should be determined on the basis of Akaike's Information Criterion (AIC). Covariates other than the treatment and the time indicator may be dropped from the model based on a 5% significance level for the Type III fixed effect test. The main test will be obtained by contrasting the scores in the two treatment arms over all post-baseline time-points (F-test). The repeated measures analysis will be supplemented by a cross-sectional analysis. Graphs will display the mean score by treatment group with their 99% confidence intervals.

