6.1.2 Enrollment

Enrollment of patients to Group A or B will be done after central determination of the MGMT promoter methylation status and if the general and neurological status of the patient remains stable.

Group A: patients with MGMT promoter-unmethylated AA or GBM will be enrolled.

Group B: patients with MGMT promoter-methylated AA or GBM will be enrolled.

Group C: registration and enrollment occur at the same time, when the patient signs the informed consent form.

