8.1.2 Randomization and stratifications

No randomization or stratification will be used in this study.

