10.5.1 Missing data

Missing data is a potential major source of bias in HRQoL assessment.

In order to check the potential impact in the study, the compliance mechanism will be investigated prior to initiating the HRQoL analysis. Characteristics of patients with and without valid HRQoL data will be compared and trends over time per dropout pattern will be investigated. Model building will be used in order to investigate whether the compliance mechanism is linked to selected prognostic variables.

Once the main analysis is completed, sensitivity analyses will be undertaken to verify the robustness of the results vis-à-vis the missing data.

In case overall compliance is deemed too low (<50%), only an exploratory analysis will be performed in lieu of the main analysis.

11 Translational research

Translational research in this trial is optional.

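### The main HRQoL test in section 10.5 compares Group A with Group B, a non-randomised contrast that cannot show a change common to both; within-group change from baseline should be the main result.

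*Combined protocol and SAP*

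**What the plan says.** Section 10.5 plans a linear mixed model for HRQoL with treatment, time, their interaction and a patient random effect, and then names the main result: "The main test will be obtained by contrasting the scores in the two treatment arms over all post-baseline time-points (F-test". Section 10.4 says HRQoL will be "evaluated in a longitudinal design in all patients entered in arms A and B of the study", so the two arms can only be A and B.

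Other sections describe those arms as follows:

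- Section 8.1.2: "No randomization or stratification will be used in this study".
- Section 6.1.2: "Group A: patients with MGMT promoter-unmethylated AA or GBM will be enrolled"; Group B takes the methylated patients.
- Section 8.1.1: "We consider groups A and B exploratory and independent from each other". The backbone is radiotherapy in A and temozolomide in B, with up to 24 and 12 evaluable patients.

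The aim in section 10.2 is not comparative: "The main objective of this study is to explore the impact of combined treatment on overall global health and HRQoL". Section 10.5 also says: "Reporting of data will be mainly descriptive, as this is an exploratory analysis". Section 10.5.1 ties the missing-data work to the main analysis: "Once the main analysis is completed, sensitivity analyses will be undertaken to verify the robustness of the results".

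**The concern.** The contrast labelled main does not answer the question asked. The aim is to learn what happens to HRQoL under TG02 plus a backbone, with emphasis on fatigue, nausea/vomiting and diarrhea as expected TG02 effects. Those are effects that both groups could share.

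An A-B comparison has no TG02-free comparator. It mixes MGMT status, backbone, TG02 schedule (sections 4.1 and 4.2) and possibly TG02 dose, because the two escalations run independently. It can fail in two ways:

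- **Missed decline.** If HRQoL falls equally in both groups, the expected contrast is zero and a null result is expected however large the fall.
- **False signal.** If the groups differ at baseline and nobody changes, a contrast of post-baseline scores can be significant. Section 10.5 mentions other baseline covariates only as a possibility and does not name the baseline score.

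At stake is the reading of HRQoL in frail elderly patients. The sensitivity analyses for missing data would also be spent on a contrast that does not address the objective.

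**Working it through.** The plan gives no sample size, target effect or significance level for the main HRQoL test, so there is no planned figure to reproduce.

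**Inputs from the documents.** SD about 20 (section 10.5); at most nA = 24 and nB = 12 evaluable patients (section 8.1.1).

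**Assumptions.** Two-sided 5% level; three post-baseline visits; equal within-patient correlation ρ of 0.5 (range 0.3 to 0.7); full completion unless stated; falls of 10 and 15 points as illustrations.

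**Step 1: the A-B contrast under a shared change.** Let both groups change by δ from baseline means a and b. The contrast estimates (a + δ) − (b + δ) = a − b. The change δ drops out, and with a = b the expectation is 0 for every δ. Simulation with shared falls of 10, 15 and 20 points gave rejection in 4.7% to 5.3% of trials.

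**Step 2: precision of the A-B contrast.**

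- One visit: SE = 20 × √(1/24 + 1/12) = 7.07.
- Mean of three visits: SE = √[400 × (1 + 2ρ)/3 × (1/24 + 1/12)] = 5.16, 5.77 and 6.32 for ρ = 0.3, 0.5 and 0.7.

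**Step 3: the A-B contrast when nobody changes.** With a 10-point baseline difference and no baseline adjustment, the mean contrast rejects in 47%, 40% and 34% of simulated trials at ρ = 0.3, 0.5 and 0.7. A joint F-test over the visits rejects in 30%, 25% and 21%.

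**Step 4: within-group change at one visit.** SD of change = 20 × √[2(1 − ρ)] = 23.66, 20.00 and 15.49 for ρ = 0.3, 0.5 and 0.7. The 95% half-width is t(0.975, n − 1) × SD of change / √n. For A at ρ = 0.5 this is 2.069 × 20/√24 = 8.4.

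| n | t | Half-width, ρ = 0.3 | ρ = 0.5 | ρ = 0.7 |
|---|---|---|---|---|
| 24 (A) | 2.069 | 10.0 | 8.4 | 6.5 |
| 12 (B, or half of A) | 2.201 | 15.0 | 12.7 | 9.8 |
| 6 (half of B) | 2.571 | 24.8 | 21.0 | 16.3 |

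**Step 5: how often that interval excludes zero** (noncentral t).

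| Fall | n | ρ = 0.3 | ρ = 0.5 | ρ = 0.7 |
|---|---|---|---|---|
| 15 points | 24 | 84.5% | 94.0% | 99.5% |
| 15 points | 12 | 51.7% | 65.8% | 86.2% |
| 15 points | 6 | 24.5% | 32.1% | 48.3% |
| 10 points | 24 | 50.9% | 65.0% | 85.7% |
| 10 points | 12 | 26.7% | 35.3% | 53.2% |

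The rows for 12 and 6 patients also show half completion. That is an illustration: section 10.5.1 sets a 50% compliance threshold but does not define it by patient counts.

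**The case against.** The best defence is that little depends on this sentence. HRQoL is called exploratory in chapter 10, no sample size is claimed, and reporting is to be mainly descriptive. The planned model has time and interaction terms and the graphs are by group, so within-group change can be obtained. If overall compliance is below 50%, section 10.5.1 replaces the main analysis with an exploratory one. This stands, and it limits the weight of the point. It does not rescue the sentence: no within-group contrast is specified, the planned graphs show mean scores rather than change, and section 10.5.1 directs the sensitivity analyses at whatever is called main.

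Second, setting 5% against 94% compares tests of different hypotheses: the 5% holds by construction, and the 94% depends on a chosen 15-point fall. That is fair. The argument is the algebra in step 1; the percentages only show what the data could reveal. With a 10-point fall or half completion they are clearly lower.

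Third, within-group change has no control, and selective dropout can distort it. This is true, and the replacement text must say so.

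Finally, separate final reports per group (section 8.2) do not forbid a joint HRQoL model, and the descriptive-only statement for A and B in section 8.2.2 does not name HRQoL. Both are supporting signs of tension, not proof of contradiction.

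**Conclusion.** The concern holds. Section 10.5 designates as main a comparison that is confounded by design and blind to any change shared by both groups, so it cannot meet the objective in section 10.2. That conclusion needs no assumed number.

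The gain from the alternative does rest on assumptions: SD 20, ρ from 0.3 to 0.7, and full completion by 24 and 12 patients. On these, change at one visit is estimated to within 6.5 to 10.0 points in A and 9.8 to 15.0 in B. Precision in B is modest, and attrition would reduce it in both groups. Only the interpretation of HRQoL is affected, so this is a change that should be made rather than one on which the trial's main conclusions depend.

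**What to change.** In section 10.5, replace the sentence naming the main test with wording such as:

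> The main result will be the model-estimated mean change from baseline in global health/QoL within each group at each scheduled time-point, with 95% confidence intervals. No between-group test will be the main analysis; any comparison of A with B is descriptive. The same estimates will be given for fatigue, nausea/vomiting and diarrhea. Within-group change describes the course under the combination; it cannot separate TG02 from the backbone or the disease, and may be affected by selective dropout.

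Obtain the estimates from the planned group-by-time model, with time categorical and baseline included as a time-point, or from one model per group. The treatment terms need not be deleted. Report the number of patients contributing at each time-point. State how the 95% intervals for change relate to the 99% intervals planned for the graphs of mean scores. The sensitivity analyses in section 10.5.1 then apply to the new main result without further edits.

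The cost is wording in section 10.5 and a clearer model specification. The data and software stay the same.
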